2.3.2 Primary Effectiveness Endpoint #1 Analysis

The primary effectiveness endpoint #1 evaluates the 12-month composite success rate ($Rate_{EP}$) evaluating acceptable atrial pacing thresholds and P-wave amplitudes in de novo subjects.

The primary effectiveness endpoint #1 hypothesis is:

$H_0: Rate_{EP} \leq 80\%$ vs. $H_1: Rate_{EP} > 80\%$

where 80% is the performance goal. The $Rate_{EP}$ is the proportion of subjects who have met success criteria in the primary effectiveness endpoint #1. The acceptable ranges for sensing and pacing which define success criteria are shown in the table below:

Parameter	Acceptable values
Pacing voltage	Pacing threshold ≤ 3.0 V at 0.4 ms
P Sensitivity	P-wave amplitude ≥ 1.0 mV

Success Criteria: A subject will be considered to have met the primary effectiveness #1 endpoint if: pacing threshold voltage ≤ 3.0 V at 0.4 ms at 12-month visit and sensed P-wave amplitude is ≥ 1.0 mV at the 12-month visit.

For subjects that do not have P-wave amplitude measured due to active atrial fibrillation or atrial tachyarrhythmias or any other heart rhythm conditions or procedures which prevent sensing amplitude from being measured, success will be determined from pacing threshold only. For subjects that do not have pacing threshold measured, due to active atrial fibrillation or atrial tachyarrhythmias or any other heart rhythm conditions or procedures which prevent sensing amplitude from being measured, success will be determined from P-wave amplitude only. Subjects that do not have P-wave amplitude and pacing voltage, both of which are unobtainable due to active atrial fibrillation or atrial tachyarrhythmias or any other heart rhythm conditions or procedures which prevent sensing amplitude from being measured, will be excluded from analysis.

The $Rate_{EP}$ will be estimated as a binomial proportion and the 97.5% lower confidence bound of the $Rate_{EP}$ will be calculated using the normal approximation. The null hypothesis is rejected at the 2.5% significance level if the LCB exceeds the PG of 80%. The p-value for the one-sided Z-test will be calculated and compared to the 2.5% significance level.

Statistical Analysis Plan

The primary analysis for the primary effectiveness endpoint #1 will be based on subjects in the full analysis population. Subjects with unsuccessful implants due to reasons other than atrial pacing/sensing (e.g. cardiac anatomy) will be excluded from the analysis. Subjects who don't meet pacing/sensing success criteria at 12-months or subjects with unsuccessful implant solely due to inadequate atrial LP pacing or sensing will be counted as failures. Additionally, subjects with missing 12-month pacing threshold or P-wave amplitude data, multiple imputation will be used to impute success or failure.

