8.2.1 Primary Safety Endpoint Analyses

The primary safety endpoint evaluates the 12-month Aveir DR LP system CFR based on CEC adjudication of adverse events. A complication is defined as a device-or-procedure-related SADE, including those that prevent initial implantation (includes both Atrial LP and Ventricular LP complications and implant procedure-related complications). The primary safety endpoint hypothesis is:

$$H_0: \text{CFR} \leq 76.5\% \quad \text{vs.} \quad H_1: \text{CFR} > 76.5\%$$

where 76.5% is the performance goal.

The CFR will be estimated using a Kaplan-Meier survival analysis and the 97.5% lower confidence bound (LCB) of CFR will be calculated using the Greenwood formula. The null hypothesis is rejected at the 2.5% significance level if the LCB exceeds the Performance Goal (PG) of 76.5%. The p-value for the one-sided Z-test will be calculated and compared to the 2.5% significance level.

The primary analysis population for the primary safety endpoint analysis will be based on subjects in the full analysis population, and the analysis will be conducted on all subjects with data available for the evaluation.

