2.2.3 Survival Analyses

For time-to-event variables, Kaplan-Meier analysis will be conducted. Subjects without events will be censored at their last known event-free time point, and for subjects with events the time to the first event will be used for the analysis. Survival estimates of the data and associated 95% confidence interval will be presented using cumulative survival and its estimated standard error (Greenwood's formula).

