2.3.1 Primary Safety Endpoint Analysis

The primary safety endpoint evaluates the 12-month Aveir DR LP system CFR based on CEC adjudication of adverse events. A complication is defined as a device-or procedure-related serious adverse event (SADE), including those that prevent initial implantation (includes both Atrial LP and Ventricular LP complications and implant procedure-related complications).

The primary safety endpoint hypothesis is:

$H_0: CFR \leq 76.5\%$ vs. $H_1: CFR > 76.5\%$

where 76.5% is the performance goal (PG).

The CFR at 12 months will be estimated using the Kaplan-Meier survival analysis. The associated one-sided lower 97.5% confidence interval will also be provided (using the Greenwood variance estimates). The null hypothesis is rejected at the 2.5% significance level if the LCB exceeds the PG of 76.5%. The p-value from the one-sided Z-test will be calculated and compared to the 2.5% significance level.

The primary analysis population for the primary safety endpoint analysis will be based on subjects in the full analysis population.

Statistical Analysis Plan

To eliminate the possible impact of Covid-19 on the confirmatory safety endpoint analysis, CEC adjudicated primary safety events (SADEs) that are related or possibly related to Covid-19 will be excluded from the primary safety endpoint analysis. Subjects who have these events will be censored at the time of the event. Additional analysis with these events included will also be provided.

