2.3.3 Primary Effectiveness Endpoint #2 Analysis

The primary effectiveness endpoint #2 evaluates the 3-month AV synchrony success rate ($Rate_{AV}$) at rest while sitting using a Holter monitor in-clinic.

AV synchrony success is defined as subjects with a paced or sensed ventricular beat within 300 ms following a paced or sensed atrial beat for at least 70% of evaluable cardiac cycles.

The primary effectiveness endpoint #2 hypothesis is:

$$H_0: Rate_{AV} \leq 83\% \quad \text{vs.} \quad H_1: Rate_{AV} > 83\%$$

where 83% is the performance goal. The $Rate_{AV}$ is the proportion of subjects who met success criteria in the primary effectiveness endpoint #2.

The $Rate_{AV}$ will be estimated as a binomial proportion and the 97.5% LCB of the $Rate_{AV}$ will be calculated using the normal approximation. The null hypothesis is rejected at the 2.5% significance level if the LCB exceeds the PG of 83%. The p-value for the one-sided Z-test will be calculated and compared to the 2.5% significance level.

The primary analysis for the primary effectiveness endpoint #2 will be based on subjects in the full analysis population. Subjects with unsuccessful implant solely due to a failure to establish i2i communication at end of implant procedure will be included and imputed as failures. Subjects with unsuccessful implants due to reasons other than AV synchrony (e.g., cardiac anatomy) will be excluded from this analysis.

Statistical Analysis Plan

Additionally, among the implanted population only the AV synchrony data available for evaluation will be used.

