2.3.4 Secondary Safety Endpoint Analysis

The secondary safety endpoint evaluates the 12-month Aveir atrial LP related CFR_A based on the CEC adjudication of adverse events. The secondary safety endpoint will be tested if all the primary endpoints are met.

An atrial LP complication is defined as an atrial device- or procedure-related SADE, including those that prevent initial LP implantation. Complications that are exclusively related to the ventricular LP or its delivery/retrieval will not be considered atrial LP complications and will be excluded from this evaluation. Complications that cannot be exclusively determined to be related to the ventricular or atrial LP will be considered atrial LP complications (e.g. femoral access complications, embolism, etc.). The secondary safety endpoint hypothesis is:

H₀: CFR_A ≤ 82% vs. H₁: CFR_A > 82%

where 82% is the PG.

The CFR_A at 12 months will be calculated using the Kaplan-Meier survival analysis. The associated one-sided lower 97.5% confidence interval will also be provided (using the Greenwood variance estimates). The null hypothesis is rejected at the 2.5% significance level if the LCB exceeds the PG of 82%. The p-value from the one-sided Z-test will be calculated and compared to the 2.5% significance level.

The secondary safety endpoint analysis will be based on the subjects in the full analysis population.

To eliminate the possible impact of Covid-19 on the confirmatory safety endpoint analysis, CEC adjudicated primary safety events (SADEs) that are related or possibly related to Covid-19 will be excluded. Subjects who have these events will be censored at the time of the event. Additional analysis with these events included will also be provided.

Statistical Analysis Plan

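### Read as plain Wald and plain Greenwood bounds, the four confirmatory performance-goal tests have a true one-sided error of about 3-4%, not the stated 2.5%

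*SAP*

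**What the plan says.** Each of the four confirmatory rates is tested against a fixed performance goal, and the decision sentence is the same each time.

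- **Effectiveness #1** (SAP 2.3.2, goal 80%): the 97.5% LCB is "calculated using the normal approximation. The null hypothesis is rejected at the 2.5% significance level if the LCB exceeds the PG of 80" percent. For missing outcomes, "subjects with missing 12-month pacing threshold or P-wave amplitude data, multiple imputation will be used to impute success or failure".
- **Effectiveness #2** (SAP 2.3.3, goal 83%): also a normal-approximation bound; "The null hypothesis is rejected at the 2.5% significance level if the LCB exceeds the PG of 83" percent. Implants that failed solely because i2i communication was not established count as failures. Otherwise, "among the implanted population only the AV synchrony data available for evaluation will be used".
- **Primary safety** (SAP 2.3.1, goal 76.5%): Kaplan-Meier with Greenwood variance; "The null hypothesis is rejected at the 2.5% significance level if the LCB exceeds the PG of 76.5" percent. Protocol 8.2.1 agrees that the bound "will be calculated using the Greenwood formula".
- **Secondary safety** (SAP 2.3.4, goal 82%): the same method; "The null hypothesis is rejected at the 2.5% significance level if the LCB exceeds the PG of 82" percent. It is tested only if all primary endpoints are met.

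Each section adds a one-sided Z-test p-value to be compared with 2.5%. The visible text does not say whether its standard error uses the observed rate or the goal. It names no continuity correction and no transformation. The general survival section (SAP 2.2.3) builds intervals "using cumulative survival and its estimated standard error", which describes the plain scale.

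**The concern.** A plain normal-approximation bound takes its standard error from the observed rate. Above 50%, the binomial variance p(1-p) falls as p rises. A result that beats its goal therefore carries a smaller standard error than the goal itself implies, and the bound clears the goal too easily. The 2.5% is then a nominal level attached to z = 1.96, not the probability of a false pass.

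The excess always favours a pass, and these tests support the CE-mark claim. The unspecified Z-test adds a second problem. If it uses the variance at the goal, it can contradict the LCB for effectiveness #1 and #2 when the result is 1-2 subjects from the threshold, and the visible text does not say how to settle that.

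The multiplicity, study-success and interim sections are redacted. The point therefore concerns each test at its own stated level, not the overall error of the trial.

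**Working it through.** **Inputs.** Goals: SAP 2.3.1 to 2.3.4. Planned n: 300 (primary safety), 240 (effectiveness #1), 267 (effectiveness #2) and 300 (secondary safety), from Protocol 8.3 and SAP 2.4. Stated level: 2.5% one-sided, z = 1.96.

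**Step 1: exact error with complete data.** Find the smallest count r for which r/n - 1.96·√[(r/n)(1 - r/n)/n] exceeds the goal p0. Then compute P(X ≥ r) for X ~ Binomial(n, p0). Without censoring, plain Greenwood equals Wald, so the same calculation covers the safety endpoints.

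For effectiveness #1:

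- 203/240 = 0.8458, SE = √(0.8458 × 0.1542/240) = 0.0233, LCB = 0.8458 - 1.96 × 0.0233 = 0.8001, a pass.
- 202/240 = 0.8417 gives LCB 0.7955, a fail.
- The SE at the goal is √(0.80 × 0.20/240) = 0.0258, larger than the 0.0233 used.
- P(X ≥ 203 | 240, 0.80) = 4.19%.

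| Endpoint | Goal | n | Smallest pass | LCB there | True error |
|---|---|---|---|---|---|
| Effectiveness #1 | 80% | 240 | 203 (84.6%) | 80.01% | 4.19% |
| Effectiveness #2 | 83% | 267 | 233 (87.3%) | 83.27% | 3.45% |
| Primary safety | 76.5% | 300 | 243 (81.0%) | 76.56% | 3.60% |
| Secondary safety | 82% | 300 | 258 (86.0%) | 82.07% | 3.88% |

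The stated 2.5% is not reproduced for any of the four.

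**Step 2: dependence on n.** The error moves with n because counts are discrete, and 240 is a high point: n = 239 gives 3.1% and n = 245 gives 3.0%. For primary safety, n = 299 gives 2.8%. Over plausible final sizes:

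| Endpoint | n | Median error | Range |
|---|---|---|---|
| Effectiveness #1 | 200-300 | 3.5% | 2.9-4.3% |
| Effectiveness #2 | 240-300 | 3.6% | 3.0-4.4% |
| Primary safety | 250-300 | 3.3% | 2.8-3.9% |
| Secondary safety | 250-300 | 3.5% | 2.9-4.2% |

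Across all four goals and every n from 200 to 500, the error is 2.7-4.7% and never as low as 2.5%.

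**Step 3: missing data and censoring, by simulation at the goal.** The documents give neither rate, so these are assumptions.

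- *Effectiveness #1:* n = 260-300, 8-20% missing at random, 20 imputations from a Beta posterior, Rubin pooling, 40,000 runs per case. Plain scale 3.4-3.7%; logit scale 2.2-2.4%. A separate simulation put the plain scale at 3.1-3.6%, so the exact figure depends on the imputation model.
- *Safety endpoints:* n = 300, 10-20% censoring, 80% or 100% of events within 30 days, 40,000 runs per case. Plain Greenwood 3.1-3.3% (goal 76.5%) and 3.4-3.8% (goal 82%); log-log 1.9-2.2%. With 5-20% dropout, 50% or 90% of events in month 1 and 200,000 runs per case, plain Greenwood gives 3.1-3.4% and 3.4-3.8%.

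**Step 4: the Z-test with null variance**, Z = (r/n - p0)/√[p0(1 - p0)/n].

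- Effectiveness #1: 203 gives 0.0458/0.0258 = 1.78, 204 gives 1.94 and 205 gives 2.10. So 203 and 204 pass the LCB and fail the Z-test.
- Effectiveness #2: 233 gives 1.86 and 234 gives 2.02. So 233 passes the LCB and fails the Z-test.

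With the estimated variance the two criteria agree.

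**Step 5: alternative bounds at planned n, complete data.**

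| Endpoint | Wilson | Clopper-Pearson |
|---|---|---|
| Effectiveness #1 | 205, 1.90% | 205, 1.90% |
| Effectiveness #2 | 234, 2.30% | 234, 2.30% |
| Primary safety | 244, 2.61% | 245, 1.85% |
| Secondary safety | 260, 1.85% | 260, 1.85% |

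Clopper-Pearson needs 1-2 more successes than Wald at every n from 200 to 500.

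**The case against.** The arithmetic is not in dispute. The objections concern the reading, the importance and the remedy.

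- **The plain scale is inferred.** The SAP names neither a variance form nor a scale, and Greenwood variance is also the input to a log-log bound. This stands as a condition on the finding. SAP 2.2.3 favours the plain reading, and nothing visible points to a transformed one.
- **A null-variance Z-test could remove the excess.** If that test also had to pass, the error for effectiveness #1 and #2 would be 1.9% and 2.3% at the planned n, and about 1.7-2.7% over n = 200-300. But the rejection sentence names only the LCB, so the Z-test is not a stated co-requirement.
- **The effect is one or two subjects.** At planned n, the move from Wald to Clopper-Pearson changes the verdict only at 203-204/240, 233/267, 243-244/300 or 258-259/300. Asymptotic bounds are also a common, openly specified choice. This limits the importance but does not make the stated level correct. SAP 2.2.2 already names the exact method for descriptive proportions.
- **Secondary safety is gated.** Since it is tested only after all primary endpoints pass, its 3.9% at n = 300 is an upper limit on its false-claim rate. This stands.
- **Wilson also exceeds 2.5% at some n.** True: it ranges over 1.7-2.7% for n = 240-300 at the 83% goal. Only Clopper-Pearson guarantees the level for a binomial count.

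**Conclusion.** The concern holds. On the plain-scale reading, every one of the four tests exceeds its stated 2.5%: by 0.9 to 1.7 percentage points at the planned n with complete data, and by a smaller or larger amount at other n, but always in the same direction. Under the assumed missing-data and censoring patterns the error is about 3.1-3.8%, which is roughly 25-50% above the stated level (3.1/2.5 = 1.24; 3.8/2.5 = 1.52).

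The complete-data figures are exact. The multiple-imputation and censoring figures rest on assumed rates, event timing and imputation model. The effect is modest and matters only close to a threshold. Even if a different reading was intended, the visible text leaves the variance and scale open and does not give one unambiguous decision rule per endpoint. The plan should be corrected, but this is not a fatal flaw.

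**What to change.** Amend SAP 2.3.1 to 2.3.4 and Protocol 8.2.1 to 8.2.4 to name the bound for each endpoint:

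- **Effectiveness #2:** a Clopper-Pearson one-sided 97.5% lower bound, with the i2i failures counted as failures. Its error is 1.6-2.5% for n = 240-300. Wilson (1.7-2.7%) is acceptable if a small excess at some n is tolerated and stated.
- **Effectiveness #1:** pool the imputed results on the logit scale and back-transform the lower bound (2.2-2.4% in simulation).
- **Both safety endpoints:** a log-log transformed Greenwood bound (1.9-2.2% in simulation).
- **All four:** define the p-value as the test that inverts the chosen bound, so that bound and p-value cannot disagree.

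The cost is wording and a software option, with no new data or patients. The tests become slightly conservative and need about 1-2 more successes each. Secondary safety power at the protocol's 90% rate falls from P(X ≥ 258 | 300, 0.90) = 98.9% to P(X ≥ 260 | 300, 0.90) = 97.5% (complete data, Clopper-Pearson count). The planning rate for effectiveness #1 is redacted. In simulation with n = 280 and 14% missing, its power falls from 99.5% to 99.1% if the true rate is 90%, from 86.4% to 81.0% at 87%, and from 57.1% to 48.6% at 85%.

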4.1.2.1 Rationale for Selection of the Primary Effectiveness Endpoint #1

The primary effectiveness endpoint #1 evaluates the ability of the atrial leadless pacemaker to pace and sense according to the intended use. The evaluation of a composite success rate of acceptable pacing thresholds and sensing amplitudes is consistent with the primary effectiveness endpoints used in the Leadless II IDE trial (Phase 1: NCT02030418 and Phase 2: NCT04559945) and multiple pre-market leadless pacemaker trials. This endpoint evaluates the atrial LP performance only since the ventricular LP performance is evaluated in the Leadless II IDE trial – Phase 2. The 12-month timepoint for assessing the primary effectiveness endpoint#1 is an appropriate time period since these electrical measurements have been demonstrated to be stable starting as early as 2 weeks post-implant based on data from the Leadless II IDE trial (Phase 1).⁹

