6.2.7 Subjects with two (2) LPs implanted

Investigators will follow subjects who leave an attempted *de novo* implant procedure with two Aveir LPs implanted through a minimum of 12-months post-implant according to the clinical investigation flowchart described in Figure 6.

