6.2.8 Subjects with one (1) LP implanted

De Novo Subjects

Investigators will follow subjects who leave an attempted *de novo* implant procedure with one Aveir LP implanted through a minimum of 12-months post-implant according to the clinical investigation flowchart described in Figure 6.

The investigator must document the nature of and reasons for the unsuccessful LP implant on the Implant Form. Subjects who leave an index procedure with one LP implanted will not be eligible for re-implantation attempts of a second LP in a different chamber at a later date during the study period.

Upgrade Subjects

Investigators will follow subjects who leave an attempted *upgrade* procedure with an unsuccessfully implanted atrial LP for a period of at least 30 days to evaluate for adverse events. At the end of the 30 days, the investigator will withdraw the subject.

The investigator must document the nature of and reasons for the unsuccessful implant on the Implant Form. Subjects who have an unsuccessful upgrade will not be eligible for re-implantation attempts of an atrial LP at a later date during the study period.

Clinical Investigation Plan for Europe

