8.2.2 Primary Effectiveness Endpoint #1 Analyses

The primary effectiveness endpoint #1 evaluates the 12-month composite success rate (Rate_{EP}) of acceptable atrial pacing thresholds and P-wave amplitudes in *de novo* subjects.

Parameter	Acceptable values
Pacing voltage	Pacing threshold ≤ 3.0 V at 0.4 ms
P-wave sensitivity	P-wave amplitude ≥ 1.0 mV

The primary effectiveness endpoint #1 hypothesis is:

$$H_0: \text{Rate}_{EP} \leq 80\% \quad \text{vs.} \quad H_1: \text{Rate}_{EP} > 80\%$$

where 80% is the PG

The Rate_{EP} is the proportion of subjects who have met success criteria in the primary effectiveness endpoint #1.

Success Criteria: A subject will meet the primary effectiveness endpoint #1 endpoint if: pacing threshold voltage ≤ 3.0 V at 0.4 ms at the 12-month visit **and** the sensed P-wave amplitude is ≥ 1.0 mV at the 12-month visit.

The Rate_{EP} will be estimated as a binomial proportion and the 97.5% LCB of the Rate_{EP} will be calculated using the normal approximation. The null hypothesis is rejected at the 2.5%

Clinical Investigation Plan for Europe

significance level if the LCB exceeds the PG of 80%. The p-value for the one-sided Z-test will be calculated and compared to the 2.5% significance level.

The Sponsor will analyze the primary effectiveness endpoint #1 on both the full analysis (primary analysis) and implanted populations. In the full analysis population, subjects with unsuccessful implants due to reasons other than atrial pacing/sensing (e.g. cardiac anatomy) will be excluded from the analysis. Subjects who don't meet pacing/sensing success criteria at 12 months or subjects with unsuccessful implant solely due to unacceptable atrial LP pacing or sensing will be counted as failures. Additionally, for subjects with missing 12-month pacing threshold or P-wave amplitude data, a multiple imputation analysis will be used to impute the missing outcomes.

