associated with each pacing stimulus. The pacing stimulus may stimulate the diaphragm either directly or indirectly via the phrenic nerve.

Dislodgement: The LP separates from the endocardium after the implant procedure has been completed.

Elevated Pacing Thresholds (RV): Pacing thresholds > 2.5 V at 0.4 ms at implant. Following lead maturation at 6-8 weeks, an increase in pacing thresholds of 1.2 V at 0.4 ms or greater between visits. This definition is intended to serve as a guideline and it is understood that individual subjects may have unique situations.

Elevated Pacing Thresholds (RA): Atrial pacing thresholds > 4.0 V at 0.4ms on or after the pre-discharge assessment, or if there is an increase in atrial pacing thresholds of 1.2V at 0.4 ms or greater between visits. This definition is intended to serve as a guideline and it is understood that individual subjects may have unique situations.

Established i2i Communication: A situation at the end of an implant procedure where non-zero i2i throughput in either LP transmission direction (i.e. A2V or V2A) has been demonstrated. If any of the following situations occur, i2i communication will NOT be considered established:

- a) Implanter decides to retrieve 1 or 2 LPs and not replace them exclusively due to unacceptable i2i communication; OR
- b) Implanter deliberately programs the LPs to a non-dual chamber pacing mode due to unacceptable i2i communication; OR
- c) There is zero i2i throughput in both LP transmission directions (i.e. atrial LP to ventricular LP AND ventricular LP to atrial LP)

Intermittent or loss of i2i communication: When the subject either (a) has their Aveir DR system programmed to a non-dual chamber pacing mode at the end of any pre-discharge or follow-up visit solely due to unsatisfactory i2i communication even in the absence of untoward clinical signs, or (b) undergoes a system revision intervention due to unsatisfactory i2i communication.

Implant procedure duration: Defined as the time from delivery catheter and LP insertion to removal.

Implant success rate: Defined as the number of *de novo* subjects leaving the implant procedure with both implanted and functioning LP devices, divided by the number of subjects in whom implantation is attempted.

Inadequate Fixation: When an LP separates from the endocardium after being released from the Delivery Catheter during the implant procedure.

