Sponsor understands that the following items meet the definition of serious adverse event if they require hospitalization or prolong hospitalization, even though an invasive approach may not be necessary to resolve: AV fistula, pseudoaneurysm, blood transfusions, tricuspid valve damage, pericardial effusion, pulmonary embolus, device dislodgement, right ventricular or right atrial perforation, thrombus formation on the device, ventricular arrhythmias even if not associated with an invasive strategy to remedy.

Non-invasive means such as device re-programming do not meet the criteria for medical or surgical intervention.

Successful Implant: A subject who leaves an attempted *de novo* implant procedure with functioning atrial and ventricular LPs implanted, including established i2i communication

Clinical Investigation Plan for Europe

Successful Upgrade: A subject with a pre-existing Aveir ventricular LP who was successfully implanted with an Aveir atrial LP, and the Aveir VR LP can be programmed to a dual-chamber mode

Time to discharge: Defined as the time from introducer sheath removal to discharge.

Unanticipated (serious) adverse device effect (UADE/USADE): Any serious adverse effect on health or safety or any life-threatening problem or death caused by, or associated with, a device, if that effect, problem, or death was not previously identified in nature, severity, or degree of incidence in the investigational plan or application (including a supplementary plan or application), or any other unanticipated serious problem associated with a device that relates to the rights, safety, or welfare of subjects. [21 CFR 812.3(s)]

Unavoidable adverse event: An unavoidable AE is defined as an adverse event related to the implant procedure that is expected to occur for a projected duration in all subjects.

Undersensing: The failure of the pulse generator to sense R-waves, causing delivery of inappropriately timed, asynchronous or competitive output pulses. Undersensing can sometimes be corrected by programming the device to a more sensitive setting, i.e., decreasing the millivolt value.

Unsuccessful Implant: A subject who leaves an attempted *de novo* implant procedure without a functioning atrial or ventricular LP implanted, or where i2i communication was not established.

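### The atrial pacing/sensing endpoint excludes subjects by a system-level implant label, so some who leave with an atrial LP in place are dropped, or counted only if they fail

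*SAP*

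**What the plan says.** - **Purpose of the endpoint.** Protocol 4.1.2.1: "This endpoint evaluates the atrial LP performance only". Success means an acceptable atrial threshold and an acceptable P-wave amplitude at the 12-month visit.
- **Exclusion.** SAP 2.3.2: "Subjects with unsuccessful implants due to reasons other than atrial pacing/sensing (e.g. cardiac anatomy) will be excluded from the analysis". Protocol 8.2.2 has the same rule for the full analysis population, which is the primary analysis: "subjects with unsuccessful implants due to reasons other than atrial pacing/sensing (e.g. cardiac anatomy) will be excluded from the analysis".
- **Failures.** The sentence that follows in both documents counts two groups as failures: subjects who miss the pacing/sensing criteria at 12 months, and subjects whose implant was unsuccessful solely because of atrial pacing or sensing. Missing 12-month values are multiply imputed.
- **The label.** Protocol Appendix II defines an unsuccessful implant as leaving the procedure "without a functioning atrial or ventricular LP implanted, or where i2i communication was not established". Its definition of established i2i communication lists situations that do not qualify. One is "Implanter deliberately programs the LPs to a non-dual chamber pacing mode due to unacceptable i2i communication"; another is zero throughput in both directions. In neither has an LP been removed.
- **Follow-up.** Protocol 6.2.8 follows de novo subjects who leave "with one Aveir LP implanted through a minimum of 12-months post-implant according to the clinical investigation flowchart". Protocol 6.2.7 does the same for those who leave "with two Aveir LPs implanted through a minimum of 12-months post-implant", with no condition on i2i. Protocol 6.6.4 calls for LP performance at 12 months as set out in 6.2.5, which lists atrial capture threshold and sense amplitude.

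**The concern.** The label used to exclude is wider than the endpoint. Two kinds of de novo subject can leave with an atrial LP and still be unsuccessful implants for a reason other than atrial pacing or sensing:

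- (a) subjects with the atrial LP only, because the ventricular LP was not placed or not kept;
- (b) subjects with both LPs in place but i2i communication not established.

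For both, the protocol provides for the very measurements that define the endpoint, and the primary analysis then sets them aside. The exclusion depends on how the procedure went, which is known only after enrolment. The analysed set is therefore no longer every de novo subject with an atrial LP.

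The failure sentence adds a second problem. A subject in (a) or (b) who misses the 12-month criteria fits both the exclusion and the failure rule, and neither document says which prevails. If the exclusion prevails, these subjects disappear. If the failure rule prevails, their failures count and their successes do not.

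Protocol 1.1.2 names this endpoint as one of three that support the AAI(R) indication, so who is in its denominator should not depend on the reader.

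**Working it through.** **1. Tracing the subjects through the text**

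| Subject leaves with | Unsuccessful implant (Appendix II)? | 12-month atrial data provided for? | Endpoint #1 as written |
|---|---|---|---|
| Both LPs, i2i established | No | Yes (6.2.7) | Evaluated |
| Both LPs, i2i not established | Yes | Yes (6.2.7) | Excluded, or counted only if failing |
| Atrial LP only | Yes | Yes (6.2.8) | Excluded, or counted only if failing |
| No atrial LP, reason other than pacing/sensing | Yes | None possible | Excluded |
| No atrial LP, solely pacing/sensing | Yes | None possible | Failure |

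Rows two and three are the problem.

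**2. The plan's own figure.** Protocol 8.3 gives 240 evaluable subjects. The assumed success rate and power are blacked out, so 240 cannot be reproduced. It is used below only as the size of the analysed set, that is, after exclusions.

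**3. Pass mark.** Both documents use the normal-approximation bound, LCB = p − 1.96 × √(p(1 − p)/n), and require LCB > 80%.

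- 203/240: p = 84.58%, LCB = 80.01%. Passes.
- 202/240: p = 84.17%, LCB = 79.55%. Does not pass.

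**4. Restoring k subjects to a borderline pass of 203/240.** The documents do not give k; the values are assumptions.

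| k restored | New n | Smallest passing count | Successes needed among the k |
|---|---|---|---|
| 6 | 246 | 208 (LCB 80.04%) | 208 − 203 = 5 of 6 |
| 12 | 252 | 213 (LCB 80.06%) | 213 − 203 = 10 of 12 |
| 15 | 255 | 216 (LCB 80.29%) | 216 − 203 = 13 of 15 |
| 30 | 270 | 228 (LCB 80.12%) | 228 − 203 = 25 of 30 |

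**5. The two readings, same subjects.** Take k = 12 with 10 successes and 2 failures, beside 203/240.

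- Dropped entirely: 203/240, LCB 80.01%. Passes.
- Counted only when they fail: 203/(240 + 2) = 203/242 = 83.88%, LCB 79.25%. Does not pass.
- All evaluated: (203 + 10)/(240 + 12) = 213/252 = 84.52%, LCB 80.06%. Passes.

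The second reading pushes the rate down; the first can push it either way.

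**6. Away from the borderline.** Assume 90% in the analysed set: 0.90 × 240 = 216, LCB 86.20%.

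- Add 12 with 6 successes: 222/252 = 88.10%, LCB 84.10%. Passes.
- Add 15 with none: 216/255 = 84.71%, LCB 80.29%. Still passes.
- Add 30 with 15: 231/270 = 85.56%, LCB 81.36%. Passes.
- Add 30 with none: 216/270 = 80.00%, LCB 75.23%. Does not pass.

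From 90%, only the last of these, with a large group failing entirely, reverses the verdict.

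**The case against.** The strongest reply is that this is a matter of wording. The only example given, cardiac anatomy, suggests a device that could not be placed, and the SAP does not itself define the label. That may well be the intent, but an example does not limit a rule, and the protocol's definition is explicit. If that is the intent, the proposed sentence states it.

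A reader might infer that the exclusion inflates the success rate, because poor i2i or a difficult procedure goes with a poor atrial position. The documents do not support that. By definition these implants were not unsuccessful because of atrial pacing or sensing, and Protocol 6.2.6 ties release of an LP to acute effectiveness having been shown. Nothing in either document gives the frequency of such subjects or a lower success rate among them. If their atrial LPs work, the rule discards valid successes.

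A reader might also infer that the AAI(R) evidence is undermined because group (a) is the atrial-only configuration. Protocol 1.1.2 bases that claim on subjects implanted with the DR system, so excluding group (a) does not contradict it.

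Two further limits stand. Protocol 8.2.2 also analyses the implanted population, whose definition is blacked out, as is part of the missing-data text in SAP 2.8. Supportive analyses may include these subjects, but the primary analysis would be unchanged. And 12-month data are less assured than 6.2.7 and 6.2.8 suggest: Protocol 5.5 lists an unsuccessful implant among possible reasons for discontinuation, and 6.6 sets the visit schedule for subjects implanted with the DR system.

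**Conclusion.** The point holds as a mismatch between label and endpoint. As written, both documents remove from an atrial-only primary analysis subjects who keep an atrial LP and whose 12-month atrial result the protocol sets out to measure. The overlap with the failure sentence leaves open whether they are dropped or counted only when they fail.

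Neither the number of such subjects nor the direction of any bias can be established. The verdict against 80% turns on a few of them only when the result is already borderline, around 203 of 240. The scenarios above rest on assumed counts and success rates and show sensitivity, not an expected effect. Otherwise the consequence is lost data and a set selected on a post-enrolment event. The change should be made, since it is cheap and settles the denominator of a primary endpoint, but the documents do not show the planned test to be invalid.

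**What to change.** In SAP 2.3.2 and Protocol 8.2.2:

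1. Limit the exclusion to de novo subjects who leave the index procedure without an atrial LP for reasons other than atrial pacing/sensing.
2. State that every de novo subject who leaves with an atrial LP, including those without a ventricular LP or without established i2i communication, is evaluated under the ordinary 12-month success, failure and imputation rules.

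Carry the same definition into the sensitivity analyses in SAP 2.8. Reconcile Protocol 5.5 and 6.6 with 6.2.7 and 6.2.8, so that the follow-up of these subjects is stated in one way.

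The cost is a sentence or two in each document. No new measurement is needed beyond what 6.2.7, 6.2.8 and 6.6.4 already provide for. The downside is that the reported rate may become slightly less favourable.
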